5.7 Poolability Analyses

All investigational sites will follow the requirements of a common protocol and standardized data collection procedures and forms. The primary endpoints will be presented separately for each site using descriptive statistics. Poolability of the primary endpoints across investigational sites will be evaluated using a regression model for site. If the p-value for the site effect is <0.15, additional exploratory analyses will be performed to understand any variations in outcomes by site. Assessment of poolability by <geography (US vs. OUS) will be performed as described for site.

5.8 Safety Analyses

Adverse events (AE) will be reported for the ITT primary analysis population. AEs will be tabulated with the number of events and subjects with event for each event type and overall. Rates will be reported as the number of subjects who experience at least one event during the analysis interval out of the total number of subjects with follow-up to the beginning of the analysis interval. Serious adverse events will also be tabulated. The rate of all AEs and SAEs reported in the study will be reported.

All AEs and SAEs will also be summarized by relatedness as described above. Adverse events leading to death or study discontinuation will be provided in listing format.

All device deficiencies will be reported in listing format.

Statistical Analysis Plan		Page 11 of 11
Sponsor	Study	Version
Senseonics	A Post Approval Study to Evaluate the Long-term Safety and Effectiveness of the Eversense® Continuous Glucose Monitoring (CGM) System	1.0

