3.4. OTHER SAFETY ENDPOINTS

Other safety endpoints include:

- Rate of all device-related and insertion and removal procedure-related adverse events (serious and non-serious events) up to 27 months post-first Sensor insertion
- Rate of device breakage up to 27 months post-first Sensor insertion
- Rate of device-related and insertion and removal procedure-related serious adverse events up to 27 months post-first Sensor insertion
- Subgroup analysis of safety endpoints based on:
 - Age (<65 years vs. >65 years, minimum 40 subjects)
 - Diabetes type (I vs. II)
- Race (non-Caucasian vs. Caucasian)

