5.4. VISIT DETAILS

5.4.1. VISIT 1 - ENROLLMENT/INSERTION

Subjects will be enrolled into the study following informed consent. Screening evaluation will determine subject eligibility for Sensor insertion. No study-specific procedures may be performed prior to informed consent signature.

The Enrollment/Insertion Visit includes performing/collecting the following information:

- Demographics- including age, gender at birth, race/ethnicity, and BMI.
- Diabetes History- including type of diabetes, date of diagnosis or length of diabetes, history of DKA and severe hypoglycemia, current treatment (type of insulin and type of insulin delivery (injections or insulin pump).
- Current and Past Medical History- including concomitant prescription medications.
- Physical examination and vital signs- including height, weight, blood pressure, pulse, temperature, assessment of potential Sensor insertion sites.
- Blood samples will be drawn for the following laboratory tests:
- Hemoglobin A1C
- Point of care testing
- Urine pregnancy test- for females of childbearing capacity (defined as not surgically sterile or not menopausal for ≥ 1 year)

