2.2 Study Endpoints

The primary safety endpoint is incidence of the composite of infection, secondary procedures to remove the Sensor, or procedure-related adverse events of at least moderate severity.

The primary effectiveness endpoint is time in range, defined as glucose values between 70 mg/dL and 180 mg/dL, at 12 months compared to the first month post-first Sensor insertion.

3 Study Design

Prospective, multi-center study at up to 30 sites in the U.S. enrolling up to 400 adult subjects with diabetes (to insert 273 subjects) including at least 40 subjects ≥ 65 years to achieve at least 1400 Sensor cycles. The subjects will have one Sensor inserted by trained health care professionals approximately every 3 to 6 months dependent upon the Sensor used (90-day Eversense Sensor or 180-day Eversense E3 Sensor).

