3.1 Blinding

There is no blinding in this study.

Statistical Analysis Plan		Page 6 of 11
Sponsor	Study	Version
Senseonics	A Post Approval Study to Evaluate the Long-term Safety and Effectiveness of the Eversense® Continuous Glucose Monitoring (CGM) System	1.0

4 Sample Size Determination

At least 273 enrolled subjects will be inserted with Sensors to achieve at least 1400 Sensor cycles. Subjects will be encouraged to remain in the study up to 27 months of follow-up or after at least 1400 Sensor cycles are completed study wide.

Based on data from the PRECISE (n=81 subjects), PRECISE II (n=90 subjects), PRECISION (n=35 subjects) and PMCF (n=1686 subjects) studies, a total of 31 events occurred that would meet the definition of the primary safety endpoint in this study. With a total of 1892 subjects, this equates to an observed rate of approximately 1.6% with an associated 95% confidence interval of 1.1% to 2.3%. As there is variability associated with this sample, as evidenced by the confidence interval, a conservative expected rate of events for this study is 2.3%. The planned sample size of 1400 total cycles) with this expected rate should provide greater than 95% power for the test of the performance goal of 4%.

Meeting the performance goal of 4% for the planned sample size would require a worst-case observation of a rate of approximately 3% or less (i.e., 41 or fewer events among 1400 cycles). This result will be clinically acceptable and similar to results observed in past studies.

5 Statistical Analyses

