5.2 Analysis Populations

Primary Analysis population: The primary safety and effectiveness analyses will be based on data from all enrolled subjects in this post approval study (ITT, Intention-to-treat).

Per-Protocol Safety Analysis Population: A per-protocol (PP) population will be identified based on those subjects who met the original inclusion and exclusion criteria, have demonstrated substantial compliance with the protocol and no significant protocol deviations affecting the primary endpoints. Supportive analyses for the primary effectiveness endpoint and all secondary and exploratory analyses will be performed in the PP population.

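### Device- and procedure-related AE rates are assigned to all enrolled subjects, with no inserted-subject set, and the Sensor-life comparison of subject-level rates mixes risk per procedure with the number of Sensors (descriptive rates only)

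*SAP*

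**What the plan says.** SAP 5.8 names the population: "Adverse events (AE) will be reported for the ITT primary analysis population". The rate is the number of subjects with at least one event in the analysis interval, "out of the total number of subjects with follow-up to the beginning of the analysis interval". The same treatment carries over to related events: "All AEs and SAEs will also be summarized by relatedness as described above". Event counts are tabulated beside the rates.

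SAP 5.2 defines the set. The primary analyses are "based on data from all enrolled subjects in this post approval study (ITT, Intention-to-treat"; insertion is not required. Protocol 5.4.1 places enrollment before the eligibility decision: "Subjects will be enrolled into the study following informed consent. Screening evaluation will determine subject eligibility for Sensor insertion". SAP section 3 plans on "enrolling up to 400 adult subjects with diabetes (to insert 273 subjects", and SAP section 4 makes the smaller number a minimum: "At least 273 enrolled subjects will be inserted with Sensors to achieve at least 1400 Sensor cycles". In the text available, neither document defines a set of inserted subjects, the analysis interval or the index procedure.

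The passages on the time origin differ. Protocol 6.3.1 collects AEs from enrollment. Protocol 3.4 has the related-AE endpoint cover "serious and non-serious events) up to 27 months post-first Sensor insertion". SAP 5.1.2 counts study days from the index procedure, and SAP 5.6.3 gives the first-insertion window for serious AEs.

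SAP 5.9 applies subgroups, including 90-day versus 180-day Sensor life, to the additional safety endpoints. It uses a regression on the subgroup term, and a p-value below 0.15 may lead to exploratory analysis. The primary composite is analysed per cycle (SAP 5.6.1.1). No per-cycle rate is planned for the other related AEs.

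**The concern.** A subject who consents, is found ineligible and never has a Sensor placed cannot have an insertion, removal or device event. Counting that subject in the denominator can only lower the rate. The plan itself separates up to 400 enrolled from at least 273 inserted, so the gap could be large. Two programmers working from SAP 5.8 could reach different rates, one starting the interval at enrollment and the other at first insertion.

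The second problem does not depend on that ambiguity. Subjects on 90-day Sensors undergo about twice as many insertions and removals as subjects on 180-day Sensors over the same period. A proportion of subjects with a procedure-related AE therefore rises with the number of Sensors even when each procedure carries the same risk. Used for the Sensor-life comparison in SAP 5.9, it could suggest a device difference that is only a difference in exposure. Protocol 5.1.1.2 also expects subjects with a mixture of both types, and a subject-level split has no place for them.

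At stake are the long-term device- and procedure-related safety figures of a study whose purpose is long-term safety and effectiveness. No hypothesis test on these endpoints is involved.

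**Working it through.** SAP 5.8 states no figure to reproduce. The inputs from the documents are up to 400 enrolled, at least 273 inserted, at least 1400 cycles, and the visit schedules in Protocol 5.1.1 to 5.3. Event counts, per-cycle risks and exit fractions below are assumptions.

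**1. Denominator.** Dilution factor = inserted / enrolled.

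- 273/273 = 1
- 273/300 = 0.91
- 340/400 = 0.85
- 273/350 = 0.78
- 273/400 = 0.6825, the planned minimum inserted over the planned maximum enrolled, hence a floor

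Example: an assumed 3 subjects with a related serious AE and 273 inserted. The exact one-sided upper 95% bound is the 0.95 quantile of Beta(x+1, n−x).

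| Denominator | Rate | Upper bound |
|---|---|---|
| 273 | 3/273 = 1.1% | 2.8% |
| 300 | 3/300 = 1.0% | 2.6% |
| 350 | 3/350 = 0.86% | 2.2% |
| 400 | 3/400 = 0.75% | 1.9% |

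With no events the bound is 1.1% at 273 and 0.75% at 400. The bound comes from Protocol 8.3, which does not name the unit; the table takes it to be the subject.

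**2. Nominal Sensors per completer.**

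- 90-day only: 720/90 = 8
- 180-day only: 720/180 = 4
- Transition at Day 90, 180, 270, 360, 450, 540 or 630: 5, 5, 6, 6, 7, 7 or 8 Sensors. For example, a switch at Day 270 gives three 90-day Sensors, then 180-day Sensors at Days 270, 450 and 630, so 3 + 3 = 6.

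The plan averages 1400/273 = 5.1 cycles per inserted subject.

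**3. Subject proportion at equal per-cycle risk.** With k cycles of independent risk r, P(at least one event) = 1 − (1 − r)^k.

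| Assumed r | k = 4 | k = 8 |
|---|---|---|
| 0.5% | 2.0% | 3.9% |
| 1% | 1 − 0.99^4 = 3.9% | 1 − 0.99^8 = 7.7% |
| 2.3% | 8.9% | 17.0% |
| 6% | 21.9% | 39.0% |

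The ratio is about 2.0 at the lower risks and 39.0/21.9 = 1.8 at 6%, with no difference in risk per procedure.

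**4. Early exit.** Let F be the true risk over the full period and d the fraction exiting, both at constant hazard: h = −ln(1−F), l = −ln(1−d). The crude proportion over one interval spanning 0 to 27 months is h/(h+l) × [1 − exp(−(h+l))].

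- For F = 0.02 and d = 0.20: h = 0.0202, l = 0.2231, crude = 0.0830 × 0.216 = 0.0179, and 0.0179/0.02 = 0.90.
- For d = 0.10 the ratio is 0.95; for d = 0.30 it is 0.84 to 0.85.
- With nine 3-month intervals and the risk set taken at the start of each, the ratio is 0.98 to 0.99 over the same range of d.

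Exit therefore matters only if one interval covers all of follow-up.

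**The case against.** The strongest reply is that the plan already points to excluding never-inserted subjects. The denominator clause requires follow-up to the start of the interval. Study Day 0 is the index procedure, a date that a never-inserted subject lacks if that term means the first insertion. Protocol 3.4 and, for serious AEs, SAP 5.6.3 count from first insertion, and SAP 5.3 lets missing data drop out. This stands, and it is why dilution is a risk and not a certainty. It does not close the point: SAP 5.8 names the all-enrolled set, does not refer to the first-insertion window, and leaves the interval undefined while AEs are collected from enrollment.

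It can also be said that the proportion of subjects with an event is a legitimate patient-level risk, that Protocol 8.3 asks for binomial proportions, that event counts are tabulated too, and that the per-cycle primary composite already covers infection, secondary removal procedures and procedure-related AEs of at least moderate severity. All of this stands. It leaves mainly the milder procedure-related events without a per-cycle rate, and it does not make a subject proportion suitable for comparing Sensor types that differ twofold in number of procedures.

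A reader might go further and infer that the plan ignores unequal follow-up. The documents do not support that in general. The quoted clause removes earlier exits from later intervals, and with short intervals the effect is negligible.

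**Conclusion.** The point holds in limited form. SAP 5.8 assigns device- and procedure-related AE rates to a set that includes subjects who cannot have such events. The possible dilution runs from none (factor 1) to a floor of 0.6825. The floor assumes that 400 are enrolled, exactly 273 are inserted, and the interval starts at enrollment. A reader might take it that these rates will be understated by about a third. The documents do not support that: they give no screen-failure rate, 273 is a minimum, 400 is a maximum, and several passages favour exclusion.

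The Sensor-life problem is firmer. Subject-level procedure-related rates would differ by about a factor of two between 90-day-only and 180-day-only completers at equal risk per cycle. That figure assumes independent cycles and subjects who stay on one Sensor type to the end. Transition subjects cannot be classified at all.

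Only descriptive rates and the subgroup comparison are touched. The primary test counts cycles, to which never-inserted subjects contribute nothing. The change should be made, but the primary safety conclusion does not depend on it.

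**What to change.** In SAP 5.8 and 5.6.3:

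- Use subjects with at least one attempted Sensor insertion as the denominator for device- and procedure-related AE rates, counted from first insertion. List AEs before insertion separately.
- Keep the binomial proportion with its exact upper bound from Protocol 8.3. Beside it, report procedure-related AEs per Sensor cycle, by the Sensor type of that cycle.
- In SAP 5.9, use this per-cycle rate for the Sensor-life comparison of procedure-related AEs, so that subjects who wore both types contribute each cycle to the right group.

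As clarification only, define the analysis interval and the index procedure. A censoring-adjusted cumulative rate is optional. It would matter if one interval spans all follow-up, and it assumes that exit is unrelated to AEs, which is doubtful if subjects leave because of them.

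No new data are needed. Insertions and removals are recorded on the CRF, and insertion success is already an endpoint, so attempts are known. The cost is SAP wording, one analysis set and one more table with its programming. The downside for the sponsor is that the reported related rates may be slightly higher.

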5.9 Subgroup Analyses

Subgroup analysis of the primary safety, primary effectiveness, and additional safety endpoints will be performed for the following subgroups: sex, age (Age<median , Age≥median), race (Caucasian vs. non-Caucasian), diabetes type (I vs. II), and sensor life (90-day vs. 180-day). In addition, the rate of procedure-related adverse events will be performed for the subgroup defined by subjects receiving care from a healthcare provide with vs. without an MD degree). These analyses are intended to demonstrate consistency of results across subgroups.

Subgroup analyses will be performed using the primary analysis set. For each subgroup, a regression model will be fit that includes a fixed effect for subgroup. If the p-value for the subgroup term is less than 0.15, additional exploratory analysis may be performed to understand any variations in outcomes by subgroup.

For each subgroup analysis, the summary statistics for each subgroup level will be presented.

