Purpose:	To evaluate the long-term safety and effectiveness of the Eversense CGM System over repeat insertion and removal cycles
Primary Safety Objective:	To demonstrate the long-term safety of the Eversense CGM System
Primary Safety Endpoint:	Incidence of the composite of infection, secondary procedures to remove the Sensor, or procedure-related adverse events of at least moderate severity
Other Safety Endpoints and Analyses:	Rate of all device-related and insertion and removal procedure-related adverse events
	Rate of device breakage
	 Rate of device-related and insertion and removal procedure- related serious adverse events up to 27 months post-first Sensor insertion
	 Subgroup analysis of all safety endpoints based on: Age (<65 years vs. ≥65 years, minimum 40 subjects)
Effectiveness Objective:	To demonstrate the long-term effectiveness of the Eversense CGM System
Primary Effectiveness Endpoint:	Time in range, defined as glucose values between 70 mg/dL and 180 mg/dL, at 12 months compared to the first month post-first Sensor insertion
Effectiveness Endpoints:	Average hours of use per day
	Change in HbA1c levels at each 6-month interval
Patient Perspective Endpoint:	Patient satisfaction with CGM system use

Senseonics, Inc. Protocol #: CTP-0034, Version 10

2023

Confidential Information

Effective Date:#: 20 March

Page 5 of 43

Other Endpoints:	 Success rate of insertion and removal procedures, overall and by HCP experience (learning curve by number of cases), to evaluate training program Rate of serious adverse events based on HCP experience with the insertion and removal of Sensors (learning curve by number of cases) HCP feedback questionnaire regarding insertion/removal
Study Duration:	Study Enrollment: Approximately 36 months Patient Participation: - Approximately 27months
	Tationer articipation. Approximately 27 months
Subject Follow-up:	Patients will return to the clinic at approximately 3-month or 6-month intervals for exchange of the Sensor and for routine follow up of their diabetes. Patients will participate for up to 27 months of CGM system use or until at least 1400 cycles of Sensor use are achieved.

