Design:	Prospective, multi-center study at up to 30 sites in the U.S. enrolling up to 400 adult subjects with diabetes (to insert 273 subjects) including at least 40 subjects ≥65 years to achieve at least 1400 Sensor cycles. The subjects will have one Sensor inserted by trained health care professionals approximately every 3 to 6 months dependent upon the Sensor used (90-day Eversense Sensor or 180-day Eversense E3 Sensor).
Statistical Analysis and Study Reporting:	Statistical analysis with interim reports will be initiated per FDA PAS guidelines of every 6 months for the first 2 years and annually thereafter. Study hypotheses will be evaluated at end of study

Page 6 of 43

Effective Date:#: 20 March

ABBREVIATIONS

AE Adverse Event
BG Blood Glucose
BMI Body Mass Index

CGM Continuous Glucose Monitoring System

CFR Code of Federal Regulations

Case Report Form CRF DCF **Data Clarification Form Diabetic Keto-Acidosis** DKA **DMS Data Management System DQMP** Data Quality Management Plan eCRF electronic Case Report Form **EDC Electronic Data Capture** ΕN **European Standard** EU **European Union**

FDA Food and Drug Administration

HbA1c Hemoglobin A1c

HCP Health Care Providers (physicians, physician assistants, and/or nurse practitioners)

HHD Hand Held Device

HPA Axis Hypothalamic-Pituitary-Adrenal axis

IRB Institutional Review Board

ISO International Organization for Standardization

ISPAD International Society for Pediatric and Adolescent Diabetes

ITT Intention-to-treat
MMA Mobile Medical App
PAS Post-Approval Study
PMA Premarket Approval

PP Per Protocol
RF Radio Frequency

SAP Statistical Analysis Plan
SAE Serious Adverse Event

SMBG Self-Monitoring Blood Glucose

UADE Unanticipated Adverse Device Effect

Senseonics, Inc. Confidential Information Page 7 of 43
Protocol #: CTP-0034, Version 10 Effective Date:#: 20 March

O TABLE OF CONTENTS

1. IN	TRODUCTION, IDENTIFICATION OF THE DEVICE, AND RATIONA	LE12
1.1.	Names, Intended Use, and Description of Study Device	12
1.1.	1. Description	13
1.1.	2. Calibration	14
1.2.	Summary of Pre-clinical and Clinical Experience	15
2. Pu	rpose of this study	15
3. ST	UDY OBJECTIVES, ENDPOINTS AND HYPOTHESES	15
3.1.	Primary Safety Objective	15
3.2.	Primary Safety Endpoint	16
3.3.	Primary Safety Hypothesis	16
3.4.	Other Safety Endpoints	
3.5.	Effectiveness Objective	16
3.6.	Primary Effectiveness Endpoint	17
3.7.	Other Effectiveness Endpoints	17
3.8.	Patient Perspective Endpoint	17
3.9.	HCP Perspective Endpoint	17

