8. STATISTICAL PLAN

The statistical plan is summarized below. Additional details concerning the analyses will be provided in the Statistical Analysis Plan (SAP) for the study.

Confidential Information

Senseonics, Inc.
Protocol #: CTP-0034, Version 10

n

Page 37 of 43 Effective Date:#: 20 March

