8.3. OTHER ENDPOINTS

Safety

Other safety endpoints will be summarized using descriptive statistics appropriate to the endpoint being evaluated. There are no formal hypotheses or tests for statistical significance associated with secondary endpoints.

The rates for serious and non-serious adverse events will be summarized as binomial proportions, together with the exact, one-sided upper 95% confidence bound. These will include insertion/removal procedure-related adverse events, and rate of device breakage.

Subgroup analysis of all safety endpoints based on:

- Age (<65 years vs. >65 years, minimum 40 subjects)
- Diabetes type (I vs. II)
- Race (non-Caucasian vs. Caucasian)

Effectiveness

Effectiveness will be measured as percentage change in the percent time in range (based on hours) at one month compared to 12 months using a time in range definition of glucose values between 70 mg/dL and 180 mg/dL. The Time in Range will be summarized as the mean of the subject percentages, together with the median, standard deviation, minimum, maximum, and 25th / 75th percentiles.

Summary statistics will also be provided for the change in HbA1c levels from baseline, and average hours of use per day.

Patient Perspective

Patient satisfaction as measured by validated questionnaires (CGM satisfaction survey and Diabetes Distress Scale) administered at select visits will be reported. The patient questionnaire scores will be summarized as means, median, standard deviation, minimum, maximum, and 25th / 75th percentiles.

Page 39 of 43

Effective Date:#: 20 March

Other Endpoints

Success rates for insertion and removal procedures will be presented to evaluate the

Senseonics, Inc. Confidential Information Protocol #: CTP-0034, Version 10

effectiveness of the training program. Success rate will also be presented based on the HCP experience with insertion and removing Sensors (learning curve by number of cases). It is anticipated that approximately 30% of the insertion and removal procedures will be done by nurse practitioners and physician assistants.

The rates of serious adverse events based on HCP experience with inserting and removing Sensors (learning curve by number of cases) will be examined.

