5.10	Interim Analyses	11
5.11	Protocol Deviations	11
6	Changes from Planned Analyses	11
7	Subject Listings	11

Statistical Analysis Plan		Page 5 of 11
Sponsor	Study	Version
Senseonics	A Post Approval Study to Evaluate the Long-term Safety and Effectiveness of the Eversense® Continuous Glucose Monitoring (CGM) System	1.0

1 Introduction

This statistical analysis plan (SAP) describes the planned statistical methods to be used during the reporting and analysis of data collected under the Clinical Investigation Protocol CTP-0034. This SAP should be read in conjunction with the study clinical investigation plan (CIP) and case report forms (CRFs). This version of the SAP has been developed with respect to the Clinical Investigation Protocol Version 10, 20 March 2023. Any revisions to the protocol or CRFs that impact the planned analyses may require updates to the SAP.

2 Study Objectives

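### The protocol cuts the safety age subgroup at 65 years, but the SAP written for the same protocol version cuts age only at the median.

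*SAP*

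**What the plan says.** The protocol gives the age cut in three places. The Synopsis, under other safety endpoints, has "Age (<65 years vs. ≥65 years, minimum 40 subjects". Section 3.4 has "Age (<65 years vs. >65 years, minimum 40 subjects", and section 8.3 repeats that line under "Subgroup analysis of all safety endpoints based on". The Synopsis design entry makes the older group a recruitment goal: "including at least 40 subjects ≥65 years to achieve at least 1400 Sensor cycles".

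SAP 5.9 lists subgroups for the primary safety, primary effectiveness and additional safety endpoints. Its age entry is "age (Age<median , Age≥median", with no reason given. For each subgroup it plans a regression with a subgroup term, and a p-value below 0.15 may lead to further exploratory work. Elsewhere the SAP mentions 65 years only as the enrolment goal in section 3.

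On how the two documents relate, SAP section 1 says "This version of the SAP has been developed with respect to the Clinical Investigation Protocol Version 10, 20 March 2023" and "This SAP should be read in conjunction with the study clinical investigation plan (CIP) and case report forms (CRFs". Protocol section 8 says "Additional details concerning the analyses will be provided in the Statistical Analysis Plan (SAP) for the study".

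**The concern.** A median cut is a different definition of the age groups, not a further detail of a 65-year cut. A programmer working from SAP 5.9 would produce the median split and nothing at 65. The study would then recruit a minimum number of older subjects and report no safety result for them as a group. The 0.15 screen for age would be run on an upper group that could be mostly under 65, which dilutes any excess confined to older subjects. If the choice is left until the report is written, it is made between two age definitions in an unblinded study whose data have already been summarised in periodic interim reports.

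**Working it through.** **Comparison of the texts**

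| Item | Protocol Version 10 | SAP 1.0 |
|---|---|---|
| Age cut | 65 years (Synopsis, 3.4, 8.3) | Median (5.9) |
| Endpoints | All safety endpoints (Synopsis, 8.3) | Primary safety, additional safety, primary effectiveness |
| Minimum in older group | 40, stated within the subgroup definition | 40, stated only as an enrolment goal (3) |
| Diabetes type | I vs II | I vs II |
| Race | Caucasian vs non-Caucasian | Caucasian vs non-Caucasian |

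Race and diabetes type carry over unchanged; of the three protocol subgroups, only age is redefined. SAP 5.6.3 sends the reader to a Section 6.9 for the subgroup definitions. That section does not exist, so no other definition is supplied. The SAP names Version 10 as its basis, so a version lag does not explain the difference.

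**How far apart the cuts are (illustration)**

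Inputs from the documents: 273 inserted subjects, up to 400 enrolled, 1400 cycles, at least 40 older subjects, expected event rate 2.3%, screen at p<0.15. Assumptions: equal cycles per subject, independent cycles, one event rate for everyone under 65, no ties at the median. The number of older subjects, n, is not given, so 40, 80 and 120 are shown.

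With 273 subjects the upper half has 137. While n is at most 137, all older subjects fall in the upper half, so

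upper rate − lower rate = (n/137) × (rate in older − rate in younger).

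- n = 40: 40/137 = 29% of the excess survives; (137 − 40)/137 = 97/137 = 71% of the upper half is under 65.
- n = 80: 80/137 = 58%.
- n = 120: 120/137 = 88%.

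If all 400 permitted subjects were inserted, the upper half is 200 and the shares are 40/200 = 20%, 80/200 = 40% and 120/200 = 60%.

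**Chance that the screen flags age**

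Cycles per subject: 1400/273 = 5.13. Older cycles are therefore 205, 410 and 615 of 1400, and the median split is 703 versus 697 cycles. The rate under 65 is set at 2.3%. The rate in older subjects is assumed to be 1.5 times that (3.45%) or twice that (4.6%). With doubling, the upper-half rate is 2.3% + (n/137) × 2.3% = 2.97%, 3.64% and 4.31%. The test is a likelihood-ratio test of the binary term, by exact enumeration.

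| Older subjects | 65-year cut, 1.5× | Median, 1.5× | 65-year cut, 2× | Median, 2× |
|---|---|---|---|---|
| 40 | 32% | 19% | 61% | 28% |
| 80 | 41% | 28% | 78% | 53% |
| 120 | 43% | 40% | 82% | 76% |

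**Precision in the older group**

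At 40 subjects there are 40 × 5.13 = 205 cycles. Five events (5/205 = 2.4%) give a Clopper-Pearson one-sided 95% upper bound of 5.1%.

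**The case against.** The strongest reply is that nothing has been lost. The SAP asks to be read with the protocol, protocol 8.3 still lists the 65-year analysis, and the SAP is meant to add detail to it. This stands: the analysis has not been withdrawn, and the harm is conditional on SAP 5.9 being followed alone. It does not settle which cut governs.

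The screening probabilities also deserve little weight. The 0.15 screen appears only in the SAP, whereas protocol 8.3 treats the other safety endpoints descriptively. A flag leads only to optional exploratory work. The effect sizes are assumed, SAP 5.9 does not state the unit or form of the regression, and cycles within a subject may be correlated. Forty is a floor, and the gap narrows quickly as more older subjects enrol. All of this is fair. The point rests on the conflict in the text and on the 40-subject minimum; the figures only show that the two cuts can differ a good deal.

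Finally, the conflict itself requires only that the documents be reconciled. Adding the 65-year cut for safety follows from the protocol. Keeping the median split beside it is a choice, and it leaves two age cuts for safety in a set of unadjusted subgroup comparisons.

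**Conclusion.** The concern holds. SAP 5.9 conflicts with the protocol version it was written for, no other SAP text restores the 65-year cut, and neither document says which governs. Applied alone, SAP 5.9 would report a different group. At the floor of 40 among 273 subjects, 71% of the upper half would be under 65 and 29% of any excess in older subjects would remain visible. At 120 older subjects, 88% would remain. These shares depend on the unknown number of older subjects and on equal cycles per subject, a single rate under 65 and no ties at the median.

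The analysis is supportive and the primary safety test does not depend on it. The change should be made, but the validity of the trial does not turn on it.

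**What to change.** In SAP 5.9, add under 65 versus 65 years and over as the age subgroup for the primary safety and additional safety endpoints. Keep the median split for primary effectiveness and, labelled as supplementary, for safety. SAP section 6 already provides for an amended plan approved before analysis.

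Two small corrections can go in at the same time. SAP 5.6.3 should point to Section 5.9. The strict inequality at 65 in protocol 3.4 and 8.3 should be checked against the Synopsis, because read literally it leaves subjects aged exactly 65 in neither group. That difference may be only a PDF reading artefact.

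The cost is one added line; age is already collected at Visit 1. The drawback is imprecision if the older group stays near 40 subjects, as the 5.1% upper bound above shows, and the report should say so.
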